## 10.4. Appendix 4: Derived and Transformed Data

### 10.4.1. General

#### Multiple Measurements at One Time Point

- Mean of the measurements will be calculated and used in any derivation of summary statistics but if listed, all data will be presented.
- If there are two values within a time window the value closest to the target day for that window will be used. If values are the same distance from the target then the mean will be taken.
- Subjects having both High and Low values for Normal Ranges at any post-baseline visits for safety parameters will be counted in both the High and Low categories of “Any visit post-baseline” row of related summary tables. This will also be applicable to relevant Potential Clinical Importance summary tables.

#### Study Day

- Calculated as the number of days from randomisation date :
  - Ref Date = Missing → Study Day = Missing
  - Ref Date < Randomisation Date → Study Day = Ref Date – Randomisation Date
  - Ref Date ≥ Randomisation Date → Study Day = Ref Date – (Randomisation Date) + 1

### 10.4.2. Study Population

#### Demographics

##### Age

- GSK standard IDSL algorithms will be used for calculating age where birth date will be imputed as follows:
  - Only the year of birth will be collected. The date and month will be imputed as ‘30th June’.
- Birth date will be presented in listings as ‘YYYY’.

##### Body Mass Index (BMI)

- Calculated as Weight (kg) / [Height (m)]

### 10.4.3. Safety

#### ECG Parameters

##### RR Interval

- IF RR interval (msec) is not provided directly, then RR can be derived as :
  - If QTcB is machine read & QTcF is not provided, then :

$$RR = \left[ \left( \frac{QT}{QTcB} \right)^2 \right] * 1000$$

- If QTcF is machine read and QTcB is not provided, then:

$$RR = \left[ \left( \frac{QT}{QTcF} \right)^2 \right] * 1000$$

- If ECGs are manually read, the RR value preceding the measurement QT interval should be a collected value THEN do not derive.

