6.2. Exclusion Criteria

Participants are excluded from the study if any of the following criteria apply:

CONCURRENT CONDITIONS/MEDICAL HISTORY (INCLUDES LIVER FUNCTION AND QT DURATION CORRECTED FOR HEART RATE [QTc] INTERVAL)

1. ALT and bilirubin $>1.5 \times \text{ULN}$ (isolated bilirubin $>1.5 \times \text{ULN}$ is acceptable if bilirubin is fractionated and direct bilirubin $<35\%$).
2. Current or chronic history of liver disease, or known hepatic or biliary abnormalities (with the exception of Gilbert's syndrome or asymptomatic gallstones).
3. QT correction using Fridericia Formula (QTcF) >450 Milliseconds (msec)

NOTES:

- The QTcF is the QT interval corrected for heart rate according to Fridericia's formula (QTcF), machine-read or manually over-read.

- The specific formula that will be used to determine eligibility and discontinuation for an individual subject should be determined prior to initiation of the study. In other words, several different formulae cannot be used to calculate the QTc for an individual subject and then the lowest QTc value used to include or discontinue the subject from the trial.
- For purposes of data analysis, QTcF, will be used as specified in the Reporting and Analysis Plan (RAP).

CONCOMITANT MEDICATIONS

4. Unable to refrain from the use of prescription (i.e., or non-prescription drugs, including vitamins, herbal and dietary supplements (including St John's Wort) within 7 days (or 14 days if the drug is a potential enzyme inducer) or 5 half-lives (whichever is longer) prior to the first dose of study medication, unless in the opinion of the Investigator and ViiV Medical Monitor the medication will not interfere with the study procedures or compromise subject safety.

RELEVANT HABITS

5. History of regular alcohol consumption within 6 months of the study defined as:
 - An average weekly intake of >14 drinks for males or >7 drinks for females. One drink is equivalent to 12 g of alcohol: 12 ounces (360 milliliters [mL]) of beer, 5 ounces (150 mL) of wine or 1.5 ounces (45 mL) of 80 proof distilled spirits.
6. Urinary cotinine levels indicative of smoking or history or regular use of tobacco- or nicotine-containing products within 1 month prior to screening.

CONTRAINdicATIONS

7. History of sensitivity to any of the study medications, or components thereof or a history of drug or other allergy that, in the opinion of the investigator or Medical Monitor, contraindicates their participation.

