9.3.3. Electrocardiograms

- 12-lead ECGs will be performed with the subject in a supine or semi-supine position having rested in this position for at least 5 minutes beforehand
- Single 12-lead ECGs will be obtained at screening and on Day -1 as indicated in the Time and Events Table using an ECG machine that automatically calculates the heart rate and measures PR, QRS, QT, and QTcF intervals. If a subject experiences a QTcF >500 msec, refer to Section [8.1.2](#) for QTcF withdrawal criteria and repeat 2 ECG recordings over a brief (e.g., 5-10 minute) period (i.e., additional QTcF readings that may be necessary).

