**ECG Parameters**

- Machine read values of RR should not be replaced with derived values.

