**Corrected QT Intervals**

- When not entered directly in the eCRF, corrected QT intervals by Bazett's (QTcB) and Fredericia's (QTcF) formulas will be calculated, in msec, depending on the availability of other measurements.
- IF RR interval (msec) is provided then missing QTcB and/or QTcF will be derived as :

$$QTcB = \frac{QT}{\sqrt{\frac{RR}{1000}}}$$

$$QTcF = \frac{QT}{\sqrt[3]{\frac{RR}{1000}}}$$

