| 22                        | All Subjects | LB6                           | Listing of Urinalysis Toxicities of Grade 2 or Higher                                    |                   | SAC [1]                |
| 23                        | All Subjects | LB6                           | Listing of All Urinalysis Data for Subjects with Toxicities of Grade 2 or Higher         |                   | SAC [1]                |
| Electrocardiograms |              |                               |                                                                                          |                   |                        |
| 24                        | All Subjects | EG6                           | Listing of Abnormal ECG Findings                                                         |                   | SAC [1]                |
| 25                        | All Subjects | EG6                           | Listing of All ECG Findings for Subjects with an Abnormal Finding                        |                   | SAC [1]                |
| 26                        | All Subjects | EG4                           | Listing of ECG Values of Potential Clinical Importance                                   |                   | SAC [1]                |
| 27                        | All Subjects | EG4                           | Listing of All ECG Values for Subjects with Any Value of Potential Clinical Importance   |                   | SAC[1]                 |

| ICH : Listings         |              |                               |                                                                                   |                                                                                                    |                        |
|------------------------|--------------|-------------------------------|-----------------------------------------------------------------------------------|----------------------------------------------------------------------------------------------------|------------------------|
| No.                    | Population   | IDSL / TST ID / Example Shell | Title                                                                             | Programming Notes                                                                                  | Deliverable [Priority] |

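### The SAP derives RR from a machine-read QTcF with exponent 2; its own cube-root definition of QTcF requires exponent 3

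*SAP*

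**What the plan says.** The RR Interval rule in SAP 10.4.3 opens with the condition "IF RR interval (msec) is not provided directly, then RR can be derived as" and then gives two branches.

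- QTcB machine read, QTcF absent: RR = (QT/QTcB)² × 1000.
- "If QTcF is machine read and QTcB is not provided, then": RR = (QT/QTcF)² × 1000, printed as "RR = \left[ \left( \frac{QT}{QTcF} \right)^2 \right] * 1000".

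The rule ends with a safeguard: "Machine read values of RR should not be replaced with derived values".

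The next item, Corrected QT Intervals, gives the forward formulas for a missing QTcB or QTcF when RR is provided. QTcB is QT over the square root of RR/1000. QTcF is QT over the cube root of RR/1000.

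In the protocol, section 9.3.3 calls for an ECG machine that "automatically calculates the heart rate and measures PR, QRS, QT, and QTcF intervals". It names neither RR nor QTcB. The QTc notes in section 6.2 add: "For purposes of data analysis, QTcF, will be used as specified in the Reporting and Analysis Plan (RAP".

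**The concern.** The two corrections use different roots of RR, yet the SAP inverts both with the same exponent. Squaring undoes a square root but not a cube root. The QTcF branch looks like a copy of the Bazett branch with the variable name changed and the exponent left alone.

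A programmer who follows the SAP literally would produce wrong RR values. If those values were then used to fill in a missing QTcB, that would be wrong too. The faulty branch is also the one that fits this trial: the protocol's named machine outputs include QT and QTcF but not QTcB, which is the condition for using it if RR is not recorded.

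The values at stake are RR and QTcB in ECG listings such as "Listing of ECG Values of Potential Clinical Importance".

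**Working it through.** **Inputs.** The forward and inverse formulas come from SAP 10.4.3. The heart rates and QT values below are assumptions for illustration and are not in the documents. The percentage error in RR does not depend on QT.

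**Step 1: invert the SAP's definitions.**

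- QTcB = QT / (RR/1000)^(1/2), so QT/QTcB = (RR/1000)^(1/2) and RR = (QT/QTcB)² × 1000. This reproduces the SAP's Bazett branch.
- QTcF = QT / (RR/1000)^(1/3), so QT/QTcF = (RR/1000)^(1/3) and RR = (QT/QTcF)³ × 1000. This does not reproduce the SAP's QTcF branch, which has exponent 2.

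**Step 2: find what the printed branch returns.** Squaring QT/QTcF gives

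derived RR = 1000 × (RR/1000)^(2/3).

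This equals the true RR only when RR = 1000 msec, that is, at 60 bpm. It is too low at slower rates and too high at faster ones.

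**Step 3: put numbers in.** True RR = 60000 / heart rate. All intervals are in msec.

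| Heart rate (bpm) | Assumed QT | True RR | QTcF | RR by SAP rule | Error in RR | RR with exponent 3 |
|---|---|---|---|---|---|---|
| 50 | 400 | 1200.0 | 376.4 | 1129.2 | −5.9% | 1200.0 |
| 60 | 400 | 1000.0 | 400.0 | 1000.0 | 0% | 1000.0 |
| 70 | 385 | 857.1 | 405.3 | 902.3 | +5.3% | 857.1 |
| 80 | 375 | 750.0 | 412.7 | 825.5 | +10.1% | 750.0 |
| 90 | 360 | 666.7 | 412.1 | 763.1 | +14.5% | 666.7 |
| 100 | 350 | 600.0 | 415.0 | 711.4 | +18.6% | 600.0 |

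At 100 bpm the derived RR of 711.4 implies 60000 / 711.4 = 84.3 bpm, which disagrees with the heart rate the machine reports.

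**Step 4: consistency check.** Putting the derived RR back into the SAP's QTcF formula should return the QTcF it came from. It does not. The discrepancies for the six rows are +7.7, 0, −6.9, −13.0, −18.2 and −22.9 msec. At 100 bpm the round trip gives 392.1 instead of 415.0. This only shows that the two formulas conflict. A machine-read QTcF would not be recomputed in practice.

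**Step 5: effect on QTcB, if it is computed from the derived RR.** The square root of (derived RR)/1000 is QT/QTcF, so QTcB = QT / (QT/QTcF) = QTcF. The Bazett value always collapses to the Fridericia value.

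- At 50 bpm, QT 400: 376.4 instead of 400 / √1.2 = 365.1.
- At 100 bpm, QT 350: 415.0 instead of 350 / √0.6 = 451.8. These fall on opposite sides of the 450 msec limit for absolute QTc in SAP Appendix 6, which does not say which correction it applies to.

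**The case against.** The algebra is not in dispute. The case on the other side is that little in the trial depends on it.

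- **The branch may never be used.** It applies only when RR is missing, it is worded as something that can be done, and machine-read RR is protected. This stands. How often the rule would be used cannot be known from the documents.
- **A derived RR may not feed QTcB.** The forward formulas apply when RR is provided, while the back-calculation applies when it is not provided directly. Read strictly, the two never meet. This is a fair reading, so the QTcB figures are conditional. The opposite reading is also open, because the SAP plans to calculate both corrections when they are not entered, as far as other measurements allow.
- **No decision rests on RR or QTcB.** The protocol selects QTcF for analysis, Appendix 6 sets no limit for RR, and the only ECG summary table is of findings. The protocol's DAIDS table grades QTc by Bazett, but the SAP applies DAIDS grading to laboratory tests. The documents also do not state that RR is displayed in the ECG listings. All of this stands and limits the severity.
- **The point turns on one superscript.** It is worth confirming in the issued SAP, although nothing in the text suggests a misprint and the cube root beside it is clear.

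None of these objections makes exponent 2 correct. They limit the consequence, not the error.

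**Conclusion.** The SAP contradicts itself. Given its cube-root definition of QTcF, the printed rule for recovering RR from QTcF is wrong at every heart rate other than 60 bpm, with errors from −5.9% at 50 bpm to +18.6% at 100 bpm. This follows from the SAP's own formulas and needs no outside source. The millisecond examples also rest on assumed QT values.

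The severity is minor. Any effect is confined to derived RR values and to QTcB if it is computed from them. QTcF eligibility (above 450 msec) and withdrawal (above 500 msec) do not depend on the rule, since QTcF is already in hand whenever the branch applies. The pharmacokinetic endpoints are unaffected. ECGs are scheduled at screening and on Day −1 of each period, so none is planned after dosing within a period. The Day −1 ECGs of later periods do follow earlier doses.

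**What to change.** In SAP 10.4.3, RR Interval, change the QTcF branch to RR = (QT/QTcF)³ × 1000. Leave the QTcB branch as it is. Make the same change in any programming specification or code written from this section.

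As a check, compare each derived RR with 60000 / heart rate, since the protocol's ECG machine already calculates heart rate.

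The cost is one exponent and a simple check. The design, the data collected and the pharmacokinetic analysis do not change.

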**ECG Parameters**

- Machine read values of RR should not be replaced with derived values.

**Corrected QT Intervals**

- When not entered directly in the eCRF, corrected QT intervals by Bazett's (QTcB) and Fredericia's (QTcF) formulas will be calculated, in msec, depending on the availability of other measurements.
- IF RR interval (msec) is provided then missing QTcB and/or QTcF will be derived as :

$$QTcB = \frac{QT}{\sqrt{\frac{RR}{1000}}}$$

$$QTcF = \frac{QT}{\sqrt[3]{\frac{RR}{1000}}}$$

**AEs****AEs OF Special Interest**

- Hypersensitivity reaction (HSR) and rash
- Liver Events
- Renal Function
- Creatine Phosphokinase (CPK) elevations

## 10.5. Appendix 5: Premature Withdrawals & Handling of Missing Data

### 10.5.1. Premature Withdrawals

| Element | Reporting Detail                                                                                                                                                                                                                                                                                                                                                                                                                                                |
|---------|-----------------------------------------------------------------------------------------------------------------------------------------------------------------------------------------------------------------------------------------------------------------------------------------------------------------------------------------------------------------------------------------------------------------------------------------------------------------|
| General | 
 
Subject study completion (i.e. as specified in the protocol) was defined as completing all phases of the study including the follow-up visit.
 
Withdrawn subjects may be replaced in the study.
 
All available data from subjects who were withdrawn from the study will be listed and all available planned data will be included in summary tables and figures, unless otherwise specified.
 
 |

### 10.5.2. Handling of Missing Data

| Element  | Reporting Detail                                                                                                                                                                                                                                                                                                                                                                                                                                                                                                                                    |
|----------|-----------------------------------------------------------------------------------------------------------------------------------------------------------------------------------------------------------------------------------------------------------------------------------------------------------------------------------------------------------------------------------------------------------------------------------------------------------------------------------------------------------------------------------------------------|
| General  | 
 
Missing data occurs when any requested data is not provided, leading to blank fields on the collection instrument : 
 
These data will be indicated by the use of a “blank” in subject listing displays. Unless all data for a specific visit are missing in which case the data is excluded from the table.
 
Answers such as “Not applicable” and “Not evaluable” are not considered to be missing data and should be displayed as such.
 
 
 
 |
| Outliers | 
 
Any subjects excluded from the summaries and/or statistical analyses will be documented along with the reason for exclusion in the clinical study report.
 
                                                                                                                                                                                                                                                                                                                                         |

#### 10.5.2.1. Handling of Missing Dates

| Element | Reporting Detail                                                                                                                                                                                                                                                                                                                                                                                                                                                                                                                                                                                                                                                                                                                                                                                                                                                                                                                                                                                                                                    |
|---------|-----------------------------------------------------------------------------------------------------------------------------------------------------------------------------------------------------------------------------------------------------------------------------------------------------------------------------------------------------------------------------------------------------------------------------------------------------------------------------------------------------------------------------------------------------------------------------------------------------------------------------------------------------------------------------------------------------------------------------------------------------------------------------------------------------------------------------------------------------------------------------------------------------------------------------------------------------------------------------------------------------------------------------------------------------|
| General | Partial dates will be displayed as captured in subject listing displays.                                                                                                                                                                                                                                                                                                                                                                                                                                                                                                                                                                                                                                                                                                                                                                                                                                                                                                                                                                            |
| AEs     | 
 
The eCRF allows for the possibility of partial dates (i.e., only month and year) to be recorded for AE start and end dates; that is, the day of the month may be missing. In such a case, the following conventions will be applied for calculating the time to onset and the duration of the event: 
 
Missing Start Day: First of the month will be used unless this is before the start date of study treatment; in this case the study treatment start date will be used and hence the event is considered On-treatment as per Appendix 2: Treatment States and Phases.
 
Missing Stop Day: Last day of the month will be used, unless this is after the stop date of study treatment; in this case the study treatment stop date will be used.
 
 
 
Completely missing start or end dates will remain missing, with no imputation applied. Consequently, time to onset and duration of such events will be missing.
 
 |

| Element | Reporting Detail                                                                                                                                                            |
|---------|-----------------------------------------------------------------------------------------------------------------------------------------------------------------------------|
|         | 
 
Start or end dates which are completely missing (i.e. no year specified) will remain missing, with no imputation applied.
 
 |

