#### 10.2.1.2. Treatment States for AE Data

| Treatment State                              | Definition                                                                                                                                                                                                 |
|----------------------------------------------|------------------------------------------------------------------------------------------------------------------------------------------------------------------------------------------------------------|
| Pre-Treatment                                | AE Start Date $<$ Study Treatment Start Date                                                                                                                                                               |
| On-Treatment                                 | If AE onset date is on or after treatment start date & on or before treatment stop date with 7 days lag time.
Study Treatment Start Date $\leq$ AE Start Date $\leq$ Study Treatment Stop Date + 6 days |
| Post-Treatment                               | If AE onset date is after the treatment stop date with 6 days lag time.
AE Start Date $>$ Study Treatment Stop Date + 6 days                                                                            |
| Onset Time Since 1 st Dose (Days) | If Treatment Start Date $>$ AE Onset Date = AE Onset Date – Treatment Start Date
If Treatment Start Date $\leq$ AE Onset Date = AE Onset Date – Treatment Start Date + 1
Missing otherwise.          |
| Duration (Days)                              | AE Resolution Date – AE Onset Date + 1                                                                                                                                                                     |
| Drug-related                                 | If relationship is marked 'YES' on eCRF OR value is missing.                                                                                                                                               |

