| Concomitant Medications | 
 
Partial dates for any concomitant medications recorded in the eCRF will be imputed using the following convention: 
 
If the partial date is a start date, a '01' will be used for the day and 'Jan' will be used for the month
 
If the partial date is a stop date, a '28/29/30/31' will be used for the day (dependent on the month and year) and 'Dec' will be used for the month.
 
 
 
The recorded partial date will be displayed in listings.
 
                                                                                                                                                                                                                                                                                                                                      |
| AEs                     | 
 
Any partial dates for AEs will be raised to data management. If the full date cannot be ascertained, the following assumptions will be made: 
 
If the partial date is a start date, a '01' will be used for the day and 'Jan' will be used for the month.
 
However, if these results in a date prior to Week 1 Day 1 and the event could possibly have occurred during treatment from the partial information, then the Week 1 Day 1 date will be assumed to be the start date.
 
The AE will then be considered to start on-treatment (worst case).
 
If the partial date is a stop date, a '28/29/30/31' will be used for the day (dependent on the month and year) and 'Dec' will be used for the month.
 
 
 
The recorded partial date will be displayed in listings.
 
 |

| Element                                                          | Reporting Detail |
|------------------------------------------------------------------|------------------|
| 10.6. Appendix 6: Values of Potential Clinical Importance |                  |

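### With a known onset after dosing and a missing stop day, the AE stop-date cap in SAP 10.5.2.1 gives a duration of zero or less

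*SAP*

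**What the plan says.** SAP 10.5.2.1 deals with AE dates for which only the month and year are known. Its conventions are meant "for calculating the time to onset and the duration of the event". A missing stop day becomes the last day of the month, "unless this is after the stop date of study treatment; in this case the study treatment stop date will be used". A missing start day becomes the first of the month, or the treatment start date if that is later.

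SAP 10.2.1.2 defines duration as "AE Resolution Date – AE Onset Date + 1". It classes an AE as On-Treatment if it starts no later than "Study Treatment Stop Date + 6 days".

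SAP 10.5.2.2 also covers AEs with partial dates. It begins with a query: "Any partial dates for AEs will be raised to data management". If the full date cannot be found, then for a stop date a month-end day "will be used for the day (dependent on the month and year) and 'Dec' will be used for the month". There is no cap at the treatment stop date. For a start date that would otherwise fall too early, "then the Week 1 Day 1 date will be assumed to be the start date".

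The protocol gives one dose per period (5.2) and no treatment after the study (7.6). AEs are collected until follow-up (9.1.1), which takes place 7 to 10 days after the final dose (5.2), and are followed to resolution or stabilisation (9.1.3).

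**The concern.** A cap at the end of treatment may do little harm when dosing lasts for weeks and most events start while it continues. Here treatment lasts for one dose. The cap therefore moves the end of an AE back to a dosing date even when the AE is known to have started later. The imputed end then comes before the recorded start, and it can fall in an earlier month than the one the site entered.

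What is at stake is AE duration, which the SAP prespecifies as a derived variable. A programmer who follows 10.5.2.1 exactly will produce impossible values for it.

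**Working it through.** **Inputs.** Duration = resolution - onset + 1 (SAP 10.2.1.2). The stop day is imputed by SAP 10.5.2.1. Let S be the treatment stop date, which is a dosing date (Protocol 5.2 and 7.6). Let onset be a complete date, S + k. The plan states no figure of its own to reproduce.

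**Does the cap always apply?** For k of 1 or more, yes. The recorded stop month cannot be earlier than the onset month, so its last day is on or after onset and therefore after S.

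**Duration.** S - (S + k) + 1 = 1 - k.

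| Onset, days after S | 0 | 1 | 2 | 6 | 10 |
|---|---|---|---|---|---|
| Duration, days | 1 | 0 | -1 | -5 | -9 |

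Days 1 to 6 lie inside the On-Treatment window. Day 10 is the latest scheduled follow-up day. An enumeration of 365 dosing dates x 10 onset offsets (k = 1 to 10) x 2 stop months (the onset month or the next) gives 7,300 cases. The cap applied in all of them, and the largest duration was 0.

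**Worked dates (assumed for illustration).**
- S = 15 May, onset 17 May, stop recorded as May. Capped: 15 - 17 + 1 = -1 day. Month-end: 31 - 17 + 1 = 15 days.
- S = 28 May, onset 1 June, stop recorded as June. Capped: the stop becomes 28 May, a month earlier than recorded, and the duration is -4 + 1 = -3 days. Month-end: 30 - 1 + 1 = 30 days.
- Onset on the dosing day, S = 15 May, stop recorded as May. Capped: 15 - 15 + 1 = 1 day. Month-end: 31 - 15 + 1 = 17 days. On the per-period reading, a dosing-day AE with a missing stop day always gets 1 day, whatever its true length.

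**Per-period or study-wide stop date.** SAP 10.2.1 and 10.2.1.2 do not say which applies. Take assumed doses on 10, 17 and 24 May, with S = 24 May study-wide. Onset on 25 May gives 24 - 25 + 1 = 0 days, and onset on 26 May gives -1. An AE from an earlier period, with onset on 12 May and stop recorded as May, stays positive but is shortened: 24 - 12 + 1 = 13 days against 31 - 12 + 1 = 20. So the 1 - k result holds on either reading for onsets after S; the readings differ only in which AEs fall after S.

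**Both days missing.** With one dose on 15 May and both dates recorded as May, the start becomes 15 May and the stop becomes 15 May, giving 1 day. With S = 28 May and both dates recorded as June, the start becomes 1 June and the stop 28 May, giving -3 days. The duration is therefore unreliable but need not be zero or negative.

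**The case against.** **Scope.** A reader might infer that every AE starting after the dose and lacking a stop day gets a duration of zero or less. The documents do not support that. SAP 10.5.2.1 also imputes missing start days, and the first both-days-missing case above comes out at 1 day. The 1 - k result needs a complete onset date. This objection stands, and the point is limited accordingly.

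**Two conflicting rules.** A reader might also infer that 10.5.2.1 and 10.5.2.2 contradict each other on the same partial date. That is not established. Section 10.5.2.1 is confined to dates with month and year known. Section 10.5.2.2 supplies both a day and a month, which is what a date with a missing month needs, so the two can be read as dividing the work. Section 10.5.2.2 does not limit itself in that way, however. Taken literally on an AE with onset 17 May and stop recorded as May, it would impute 31 December: 14 days to the end of May, plus 30 + 31 + 31 + 30 + 31 + 30 + 31 = 214, plus 1, or 229 days. The month-end figures above use the recorded month and are not a literal output of 10.5.2.2. A clarification is justified; a charge of contradiction is not.

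**Consequence.** Subjects stay in the unit from Day -1 until discharge in each period (Protocol 2.2), so partial dates should be few. They are queried, and cleaning is finished before database freeze (SAP 3.1). Listings show the date as recorded: "Partial dates will be displayed as captured in subject listing displays". All of this stands and limits the size of the point. It does not make the cap correct.

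**Conclusion.** The cap in SAP 10.5.2.1 is a wrong rule for this design, not a missing detail. For a complete onset date k of 1 or more days after the treatment stop date and a missing stop day, it always gives 1 - k days. This rests only on the SAP's formula, the one-dose-per-period design, and a recorded stop month no earlier than onset.

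The severity is minor. It would be tempting to conclude that the safety summaries are distorted, but the documents do not support this. Treatment state is assigned from the AE start date (SAP 10.2.1.2), and none of the AE tables listed in SAP 10.10.4 summarises duration. Whether an AE listing prints the derived duration depends on a template that the documents do not show. The PK endpoints do not use these dates.

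Month-end is still an imputation. With a known onset it gives the longest duration compatible with the recorded month, not an estimate of the true one. It does avoid a stop before the start and a stop outside the recorded month.

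**What to change.** In SAP 10.5.2.1, remove the cap at the treatment stop date. Set a missing stop day to the last day of the recorded month. Optionally, limit it to the subject's last study contact when that contact falls in the recorded month, and define that contact if the option is used. Never let the imputed stop precede onset. For the AE with onset 17 May, a last contact on 25 May would give 25 - 17 + 1 = 9 days. Without the cap, the stop-date imputation no longer depends on whether treatment stop is per period or study-wide.

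As clarifications only:
- State that 10.5.2.1 governs dates with a missing day and 10.5.2.2 those with a missing month, so that December is used only when the month itself is unknown.
- Replace Week 1 Day 1, which is not in this schedule, with Period 1 Day 1, the term used under Treatment Assignment in SAP 2.3.

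Partial start dates should not be tied to each period's dose date unless the SAP also says which dose applies. With a washout of about 7 days, a Part 2 subject can have three doses in one calendar month.

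The cost is a few lines of SAP text and a small change to the AE date derivation. No new procedure or assessment is needed.
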